5.1. Definition

Unexpected events that have not been defined as endpoints (section 4) or expected complications of the PCI procedure (listed in PCI definitions, section 13.4) should be reported as either a serious adverse event (SAE) or non-serious adverse event (NSAE) depending on their severity.

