5.2. Unexpected Serious Adverse Events

SAEs should be reported to the Clinical Trials Unit (CTU) within 7 days. The report should include an assessment of causality by the Principal Investigator at each site (see section 5.4.2). The Chief Investigator will be responsible for the prompt notification of findings that could adversely affect the health of patients or impact on the conduct of the trial.

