5.3. Unexpected Non-Serious Adverse Events

Unexpected NSAEs should be evaluated by the Principal Investigator. This should include an assessment of causality (see section 5.4.2) and intensity (see section 5.4.1) and reports made within 14 days. The CTU will keep detailed records of all unexpected adverse events reported. Reports will be reviewed by the Chief Investigator to consider intensity, causality and expectedness.

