5.4. Reporting unexpected adverse events

Investigators will make their reports of all unexpected adverse events, whether serious or not, to the CTU at the London School of Hygiene & Tropical Medicine.

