5.4.1. Assessment of intensity

Mild: The patient is aware of the event or symptom, but the event or symptom is easily tolerated.

Moderate: The patient experiences sufficient discomfort to interfere with or reduce his or her usual level of activity.

Severe: Significant impairment of functioning; the patient is unable to carry out usual activities and/or the patient's life is at risk from the event.

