5.4.2. Assessment of causality

Probable: A causal relationship is clinically / biologically highly plausible and there is a plausible time sequence between onset of the adverse event and the PCI procedure / commencement of OMT.

Possible: A causal relationship is clinically / biologically plausible and there is a plausible time sequence between onset of the adverse event and the PCI procedure / commencement of OMT

Unlikely: A causal relationship is improbable and another documented cause of the adverse event is most plausible.

Unrelated: A causal relationship can definitely be excluded and another documented cause of the adverse event is most plausible.

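### Protocol section 5.1 separates SAEs from NSAEs by severity and gives no seriousness criteria, so a related event needing admission can be filed as an NSAE, outside the section 5.5 notification

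*Protocol*

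**What the plan says.** Section 5.1 of the protocol, headed Definition, covers unexpected events that are neither section 4 endpoints nor PCI complications listed in 13.4. It says these "should be reported as either a serious adverse event (SAE) or non-serious adverse event (NSAE) depending on their severity".

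The class then sets the route:

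- **SAE (5.2):** report to the CTU within 7 days, with the Principal Investigator's causality assessment. "The Chief Investigator will be responsible for the prompt notification of findings that could adversely affect the health of patients".
- **NSAE (5.3):** the Principal Investigator evaluates the event. "This should include an assessment of causality (see section 5.4.2) and intensity (see section 5.4.1) and reports made within 14 days". On central review: "Reports will be reviewed by the Chief Investigator to consider intensity, causality and expectedness".
- **Notification (5.5):** the CTU informs the Sponsor, the REC and the DSMC of reported SAEs that the Chief Investigator has classed as unexpected and as Probable or Possible in causality.

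The only graded scale for an event's severity is in 5.4.1, where it is called intensity. Mild reads "The patient is aware of the event or symptom, but the event or symptom is easily tolerated". Moderate reads "The patient experiences sufficient discomfort to interfere with or reduce his or her usual level of activity". Severe covers inability to carry out usual activities or risk to life. Section 16.3.2 repeats the 7- and 14-day limits and refers back to section 5.

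**The concern.** Severity and seriousness are different properties. Severity grades how intense an event is. Seriousness depends on its outcome or on what had to be done: threat to life, admission or longer admission, lasting disability. Section 5.1 names the first as the rule for sorting events into classes that are named after the second.

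The class sets both the deadline and whether the Sponsor, REC and DSMC must be told. In an open trial of an invasive procedure against medical therapy, sites that know the allocation would be applying an undefined rule. What the DSMC receives under 5.5, and the SAE proportions by arm planned in section 10.1 of the main SAP, would then partly reflect how each site reads one word.

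**Working it through.** The plan states no figure on this point, so the check sets the sections side by side.

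**1. Is seriousness defined anywhere?** Sections 5.1 to 5.5, 16.3.2 and the glossary contain no outcome-based criteria. Section 7.2 commits the trial to Good Clinical Practice in general terms without listing any. Section 10.1 of the main SAP only says that AEs and SAEs will be reported as proportions.

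**2. What could a site use for severity?** The one graded scale is 5.4.1. It rests on functional impact and risk to life and does not mention admission. Its top grade is called Severe, so a site looking for a severity rule may well go there. The protocol does not state that link.

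**3. Trace one event.** Take a minor ischaemic stroke with mild deficits after PCI that leads to or prolongs admission.

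- *Section 4:* not an endpoint. Intracranial haemorrhage falls under major bleeding (type 3c), but ischaemic stroke is not listed.
- *Section 13.4:* not among the listed PCI complications. The event is therefore within the scope of 5.1.
- *Section 5.4.1:* could be graded Mild or Moderate.
- *Section 5.4.2:* at least Possible, if the site judges that "A causal relationship is clinically / biologically plausible and there is a plausible time sequence".
- *Section 5.1:* if severity is read as 5.4.1 intensity, it can be filed as an NSAE.
- *Sections 5.3 and 16.3.2:* the limit is 14 days instead of 7, so 14 − 7 = 7 days longer.
- *Section 5.5:* not triggered, because it covers only reported SAEs.

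**4. Would a later step catch it?** The Chief Investigator's review in 5.3 covers intensity, causality and expectedness, not seriousness. The visit lists in 16.2 prompt for unexpected SAEs but have no NSAE item, and they list general hospitalisation at one site only. Section 17 collects inpatient days for the economic analysis, which is not a safety-notification route. No stated step reclassifies the event.

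**5. What still works?** Section 5.4 says "Investigators will make their reports of all unexpected adverse events, whether serious or not, to the CTU". The event therefore reaches the CTU and the Chief Investigator, whose general duty in 5.2 remains. What is lost is the shorter deadline and the defined 5.5 notice.

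**The case against.** The strongest reply is that the authors simply meant seriousness. The classes are called serious and non-serious. Section 5.1 says severity while 5.4.1 says intensity, and nothing joins the two. Section 5.3 also asks for intensity on events already classed as NSAEs, using a scale that includes Severe; if intensity decided the class, that grade could not occur there. The commitment to Good Clinical Practice is a further reason to read serious in its ordinary trial sense. The SAE and NSAE forms mentioned in 16.3.2 are not shown and may carry the criteria. A patient kept in hospital may also be graded Severe as unable to carry out usual activities, and a site may be reluctant to call any stroke non-serious.

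Much of this stands. It makes the harm conditional, and it rules out three things that a reader might infer:

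- **That the protocol defines an SAE by the 5.4.1 scale.** It does not say so.
- **That events have been misfiled.** The documents give no evidence of it.
- **That such events escape oversight altogether.** They still go to the CTU and the Chief Investigator.

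The reply does not remove the fault in the text. A section headed Definition states the wrong property as its rule, and nothing readable supplies the right one. The structure of 5.3 suggests what was intended, but a site has to infer it.

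**Conclusion.** The point holds as a wrongly stated safety rule with a conditional consequence. If a site reads severity as 5.4.1 intensity, an unexpected event of mild or moderate intensity that requires or prolongs admission, with Possible or Probable causality, can be filed as an NSAE. It then has a limit 7 days longer and falls outside the 5.5 notice.

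This rests on three assumptions: that at least some sites use the intensity scale, that the forms do not supply seriousness criteria, and that the Chief Investigator would class the event as unexpected, as 5.5 also requires. If either of the first two fails, nothing is lost.

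The documents do not allow the number of events to be derived. An event graded Severe is not at issue, since it would be an SAE on the intensity reading. Deaths, heart failure admissions, the other section 4 endpoints and the listed PCI complications are captured separately, so the primary analysis is unaffected. The change should be made because it is cheap and concerns safety reporting, not because harm has been shown.

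**What to change.** - **Section 5.1:** replace the severity clause with a rule such as: *An event is an SAE if it is life-threatening, requires or prolongs hospital admission, causes persistent or significant disability, or is otherwise medically important; all other events are NSAEs.* Death need not be listed here, as it is already an endpoint.
- **Section 5.1 or 5.4.1:** state that intensity is a separate descriptor and does not decide the class.
- **Section 5.3:** add seriousness to the items that the Chief Investigator reviews, so that a misfiled event can be reclassified and notified under 5.5.
- **Optional:** a desk check of NSAE forms already held at the CTU against the new criteria. The documents do not show that it is needed.

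The cost is a few words in section 5 and slightly more SAE forms and 5.5 notices. No new visits or patient data are needed.

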5.2. Unexpected Serious Adverse Events

SAEs should be reported to the Clinical Trials Unit (CTU) within 7 days. The report should include an assessment of causality by the Principal Investigator at each site (see section 5.4.2). The Chief Investigator will be responsible for the prompt notification of findings that could adversely affect the health of patients or impact on the conduct of the trial.

5.3. Unexpected Non-Serious Adverse Events

Unexpected NSAEs should be evaluated by the Principal Investigator. This should include an assessment of causality (see section 5.4.2) and intensity (see section 5.4.1) and reports made within 14 days. The CTU will keep detailed records of all unexpected adverse events reported. Reports will be reviewed by the Chief Investigator to consider intensity, causality and expectedness.

5.4. Reporting unexpected adverse events

Investigators will make their reports of all unexpected adverse events, whether serious or not, to the CTU at the London School of Hygiene & Tropical Medicine.

5.4.1. Assessment of intensity

Mild: The patient is aware of the event or symptom, but the event or symptom is easily tolerated.

Moderate: The patient experiences sufficient discomfort to interfere with or reduce his or her usual level of activity.

Severe: Significant impairment of functioning; the patient is unable to carry out usual activities and/or the patient's life is at risk from the event.

5.4.2. Assessment of causality

Probable: A causal relationship is clinically / biologically highly plausible and there is a plausible time sequence between onset of the adverse event and the PCI procedure / commencement of OMT.

Possible: A causal relationship is clinically / biologically plausible and there is a plausible time sequence between onset of the adverse event and the PCI procedure / commencement of OMT

Unlikely: A causal relationship is improbable and another documented cause of the adverse event is most plausible.

Unrelated: A causal relationship can definitely be excluded and another documented cause of the adverse event is most plausible.

5.5. Notification

The Sponsor, the Research Ethics Committee (REC) and the Data and Safety Monitoring Committee (DSMC) will be notified by the CTU when reported SAEs have been classified by the Chief Investigator as **both** unexpected and given a causality classification of either Probable or Possible.

6. Trial Population

6.1. Inclusion Criteria

ALL of the following:

- 1. Poor left ventricular function (EF ≤35%)#
- 2. Extensive coronary disease*
- 3. Viability in at least 4 dysfunctional myocardial segments that can be revascularised by PCI
- # Biplane/3D echocardiography or MRI can be used to assess the qualifying LVEF. The imaging study should be performed at least 4 weeks after a MI, if there has been a recent clinical diagnosis of a MI.
- * In general, patients who do not have bypass grafts will be eligible if they have at least proximal left anterior descending (LAD) disease or at least proximal 2 vessel disease. For patients with patent bypass grafts, or in cases where the extent of coronary artery disease (CAD) is uncertain, the BCIS-1 JS should be calculated. The maximum possible JS score is 12 and a score ≥6 is required to be eligible for REVIVED. N.B. The JS should be based on all coronary disease, not just the vessel subtending viable myocardium.

6.2. Exclusion Criteria

- 1. MI <4 weeks prior to randomisation (clinical definition as adjudicated by recruiting centres)
- 2. Acutely decompensated heart failure requiring inotropic support, invasive or non-invasive ventilation or Mechanical Circulatory Assist therapy <72 hours prior to randomisation
- 3. Sustained VT/VF or appropriate ICD discharges <72 hours prior to randomisation
- 4. Valve disease deemed by the local heart team to require imminent intervention
- 5. Contraindications to PCI
- 6. Age <18 years
- 7. Estimated glomerular filtration rate (eGFR) <25 ml/min, unless established on dialysis
- 8. Women who are pregnant
- 9. Previously enrolled in REVIVED-BCIS2 or current enrolment in other trial that may affect REVIVED-BCIS2 outcome data
- 10. Life expectancy <1 year due to non-cardiac pathology

7. Ethical Considerations

7.1. Consent

Only patients that give written consent will be included in the trial. If fully informed consent is not possible, the patient will not be recruited into the trial. The patient should be given sufficient time to consider the trial, recommended to be 24 hours, following which informed consent will be taken. Consent may be taken once all requirements for inclusion have been met.

Staff at site may telephone potential patients with information about the trial before scheduled hospital appointments. If a patient is interested, then the site can post them the information sheet to read prior to their appointment and follow this up with a further telephone call within a reasonable time frame.

A patient may decide to withdraw from the trial at any time without prejudice to their future care.

7.2. Declaration of Helsinki and Good Clinical Practice

The trial will conform to the spirit and the letter of the Declaration of Helsinki, and in accordance with Good Clinical Practice Guidelines.

7.3. Ethical committee review

The National Research Ethics Service Committee London - Westminster have reviewed and approved the trial (REC reference 10/H0802/46). Copies of the letters of approval are to be filed in the trial site files at each centre.

8. Statistical Considerations

8.1. Power Calculation

The predicted occurrence of death or hospitalisation for heart failure at two years is 36% in the OMT group(8, 19, 31, 41, 42). The primary endpoint in REVIVED-BCIS2 will be measured over the entire trial duration, with a minimum follow-up duration of two years, thus increasing the number of events. A trial of 700 (350 in each group) with 300 patients experiencing an event would have over 85% power to detect a hazard ratio of 0.7 (a 30% relative reduction in the hazard) at 5% significance allowing for up to 5% losses by the end of follow-up and increasing recruitment over time. For illustrative purposes this represents a reduction in death or hospitalisation to 27% in the PCI group at two years. The hazard ratio of 0.7 used in the power calculation is pragmatic, while being clinically meaningful and is in line with the magnitude of benefit observed across other treatment modalities in this population.

For the major secondary endpoint, even half this sample size will provide 90% power to detect a minimum difference in EF of 4%, assuming a standard deviation of 11%. The trial is expected to have very good power to detect differences in Quality of Life (one of the major secondary outcomes).

The above predicted event rates take into account the possibility of patients randomised to OMT subsequently undergoing PCI (see below). If a higher event rate is found in the OMT group or patient recruitment rates exceed expectation early in the trial (thus providing a

longer duration of follow-up in a larger proportion of patients), the trial would have greater power to detect a hazard ratio of 0.7, or alternatively, provide over 85% power to detect smaller differences in treatment effect.

Although a smaller treatment effect may be clinically significant, this would have a major impact on sample size, which in turn may affect the feasibility of completing the trial within the proposed timescale and resources.

8.2. Crossover

In patients randomly assigned to receive OMT, revascularisation by PCI or CABG during the trial should only be considered in one of the following circumstances:

- Readmission with an acute coronary syndrome (ACS), including ST-elevation myocardial infarction (STEMI) and non-STE events. The diagnosis of ACS will be based on the presence of typical ischaemic symptoms as well as a rise in cardiac biomarker levels or dynamic ST deviation on ECG.
- Deterioration in exertional angina to ≥CCS class 3 level symptoms.
- Resistant ventricular arrhythmias considered to be ischaemic in aetiology.

This trial will be a comparison of strategy, rather than technique, and the projected event rates and hazard ratio allow that OMT patients may undergo subsequent revascularisation. As such, no additional adjustments have been made to the power calculation to account for unplanned revascularisation in the OMT arm.

8.3. Statistical Analysis

A detailed statistical analysis plan will be finalised before any analysis of the data by treatment group is undertaken. An unadjusted time-to-event analysis will be performed on the primary endpoint using data across all follow-up, with time to the first event (or censoring) times measured from randomisation. Hazard ratios together with associated confidence intervals will be calculated from the Cox proportional hazards model. The assumptions underlying the Cox model will be assessed. If there is clear non-proportionality, comparisons will also be made in early and later follow-up with cut-points determined based on availability of data prior to unblinding. Cumulative event rates will be calculated and presented using Kaplan-Meier time-to-event curves. As a measure of absolute treatment difference, cumulative event rates will be compared at 2 years. Secondary analyses of each individual component of the primary composite endpoint as well as other secondary time to event outcomes will be analysed using the above methods. Losses to follow-up are expected to be minimal and patients will be included up until the time they experience the event or are censored.

Any categorical outcome measures will be examined at specific time points using risk ratios or risk differences, confidence intervals and chi-square or Fisher's exact tests as appropriate. Continuous variables will be analysed and presented as mean treatment differences, confidence intervals and p values derived from analysis of co-variance models or unpaired t-tests as appropriate (with appropriate transformation if necessary). Analysis of endpoints in the randomised cohort will be by intention-to-treat.

A limited number of subgroups for the primary endpoint will be pre-specified in the analysis plan and are likely to include groups stratified by age, the extent of coronary disease (BCIS-1 JS <12 vs. 12), degree of LV dysfunction (EF <20% vs. ≥20%), diabetes, NYHA class (<3 vs. ≥3) and chronic total occlusion (CTO). In addition, a model will be developed and patients will be categorised according to their baseline risk of the primary outcome and this will be used to examine whether the impact of treatment depends on a person's underlying risk. Since the subgroup analyses are secondary analyses and exploratory in nature, the trial has not been

powered for these. A Cox proportion hazards model incorporating tests of interaction will be used for subgroup analyses.

Other analyses such as sensitivity and per-protocol analyses will be detailed in the statistical analysis plan.

8.4. Interim Analysis

An interim analysis of recruitment and pooled event rates was performed approximately one year after the first patient was recruited to inform the feasibility of completing the trial within the initial projected period. As the number of patients randomised was still relatively small and length of follow-up short, it was felt that the expected number of events at this stage of the trial was too low for meaningful assessment. Recruitment and the pooled event rate will continue to be monitored as the trial progresses.

An independent DSMC has been established and a separate DSMC charter developed which includes details of the meeting schedule and stopping guidelines. The DSMC is expected to meet at least annually.

9. Screening

9.1. Screening population

Patients with LVEF <40% should be screened for eligibility. They may come from the following sources:

- Patients referred to the heart failure team for initiation or optimisation of medical therapy including inpatient referrals, outpatient nurse led heart failure clinics and referrals from district general hospitals.
- Patients referred for viability assessments who are known to have poor resting LV function.
- Patients referred for consideration of CRT or ICD implantation.
- Patients with poor LV function referred for consideration of revascularisation following coronary angiography.
- Patients referred for coronary angiography to establish the aetiology of a dilated cardiomyopathy, who are found to have coronary artery disease.

9.2. Screening log

Full detailed screening logs of all patients with extensive CAD and EF ≤35% considered for the trial will be completed at sites.

The CTU will collect a snapshot of screening outcomes, once a year, from all participating sites. Only patients who complete the screening process (i.e. randomised, declined, met an exclusion criterion) in that three-month period are required to be entered.

10. Assessment of LVEF

10.1. Qualifying ejection fraction

To determine eligibility for the trial, LVEF can be determined by the following modalities:

- Transthoracic echocardiogram (TTE) (Simpson's biplane on 2D or 3D echocardiography)
- The resting stage of a stress echocardiogram
- Cardiac MRI

[figure not shown]
The qualifying assessment **must** have been carried out less than 1 year before randomisation. Estimation of LVEF and adjudication of eligibility for enrolment in will be done by each participating centre, using locally agreed protocols.

